Official title :

Ambispective, Multicentre, Open-label Study Evaluating the Clinical Outcomes of Foot Surgery Using SERF Medical Devices

NCT number : NCT05672069

Document date : 10/11/2022

Title	Ambispective, Multicentre, Open-label Study Evaluating the Clinical Outcomes of Foot Surgery Using SERF Medical Devices
Sponsor	SERF [name]
Rational (or justification)	
The aim of the study is to follow patients with foot pathology. These patients undergo foot surgery with the aim of reducing their pain and restoring their ability to walk. This study will monitor changes in the patient's quality of life before and after the operation.
 
The products under investigation are CE marked under Directive 93/42/EEC with clinical data based on equivalent devices. Regulation 2017/745 requires the collection of clinical data specific to each device. Consequently, this study will collect clinical data on the performance and safety of the devices, making it possible to confirm the favourable benefit/risk profile for the patient.

Implants studies	
The devices studied in this clinical trial are as follows:
 
 - FAST plates (CE marked since 2018) - FAST screws (CE marked since 2016) - Toe FAST (CE marked since 2021) - VEOFIX screws (CE marked since 2019) 
The devices in the FAST screws, FAST plates, Toe FAST and VEOFIX screws ranges have been designed to be implanted in patients requiring repair or stabilization of elements of the foot, up to and including stabilization and fixation of the bones between them.

Population concerned	The target population for this study was any adult patient implanted with FAST screws, FAST plates, Toe FAST and VEOFIX screws between november 2021 and october 2022.
Subject population	
For each Extremity product, the number of inclusions was set at 80, giving a total of 320 subjects for this study.
 
The following selection criteria were used.
 
Inclusion criteria:
 
 - Male or female subject of legal age at the date of implantation; - Subject implanted with one or more implants: FAST Screw, FAST Plate, Toe FAST and VEOFIX Screw between November 2021 and October 2022; - Subject able to understand the information and instructions given by the investigator; - Subject with a social security affiliation. 
Exclusion criteria:
 
 - Vulnerable persons - People with contraindications (including pregnant women) 
Non-inclusion criteria:

	
As the series is observational and involves an additional procedure that is neither burdensome nor invasive, all implanted patients will be considered. However, the following patients will not be included:
 
Subjects who have not expressed their consent to the collection of their data and participation in the study.

Methodology	
Post-marketing clinical follow-up study performed according to standard care with an additional, non-burdensome, non-invasive procedure (Case 4.1) ambispective, multicentre, open-label, non-comparative. Only a quality-of-life questionnaire (AOFAS Score) and patient satisfaction will be requested in addition to standard care.

Objectives	
Primary objective:
 
 - To evaluate the reduction in patient pain and the restoration of walking. 
Secondary objectives:
 
 - To collect performance and safety data to assess the subject's outcomes and functional status.
Endpoints	
Primary endpoints:
 
American Orthopaedic Foot and Ankle Society (AOFAS) score >80 points at 12 months. This score is assessed using a questionnaire measuring the patient's pain, function and mobility of the foot. It incorporates both subjective and objective information. Patients report their pain and the doctor assesses bone alignment. The scores range from 0, the worst, to 100, the best. There are different AOFAS scores depending on the location of the implant: - AOFAS Forefoot - Hallux - AOFAS Midfoot - AOFAS Ankle/Hindfoot
 
Secondary endpoints:
 
 - Survival rate of each implants, at 12 months, to determine the Kaplan-Meier type survival curve, with any revision, whatever the cause, as the endpoint. Each inflection point will correspond to a revision surgery involving the removal or replacement of a component of the implant in question, whatever the cause of the revision. Patients who died or were lost to follow-up will be included in the analysis. - Bone consolidation rate of the cohort, the evaluation of bone consolidation at 12 months is assessed by the investigator via the following question: 'On radiographic reading, is bone consolidation satisfactory? 4 answers are proposed: 'total / partial / none / no information'. - Overall patient satisfaction will be assessed at 12 months using the following question: 'Given your expectations, are you satisfied with your operation? 4 answers are proposed: 'I am completely satisfied with the results of my operation / My condition has not improved as much as I had hoped, but I would be prepared to undergo the same operation for the same result / The operation has improved my condition, but I would not be prepared to undergo the same operation for the same result / My condition is the same or even worse than before my operation'. - Complications / effects and adverse events during and after the operation at all follow-up visits.

Data collected	The data collected for this study are: demographics, surgery details, clinical scores (AOFAS score, patient satisfaction), possible adverse events related or not to the implant.
Indirectly nominative nature of the data	Data is collected and stored in a pseudo-anonymized format that does not allow any patient to be identified through the data collected. Under no circumstances will patient names be transmitted or communicated to SERF.
Ethical consideration	CIP and associated procedures obtained an EC approbation on 18/11/2022 (CPP Nord Ouest III), prior to investigation initiation on 07/12/2022. As per its design, the investigation is submitted to an ethic committee and is reported to a Competent Authority (ANSM). This study was registered on clinicaltrials.gov public database.
Data quality assurance	A sponsor's clinical staff member will monitor collected clinical data through source data verification and source data review. A report will then be prepared.
Study-related treatment(s) / procedure(s)	Only a quality-of-life questionnaire and patient satisfaction (an additional procedure that is non-burdensome and non-invasive) are required for participation in this CI, compared with the standard care provided as part of the routine follow-up to foot surgery at each centre.
Study schedule	Study preparation: January-June 2022 Inclusion: as soon as regulatory approvals are obtained, estimated for November 2022 End of monitoring: 10/2023 CI report: Q3 2024
Study duration	The total duration of the study (inclusion + follow-up) is 2 years.
Statistical analysis	No statistical tests are planned for this CI. Only a descriptive analysis of the data is planned.

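### Does the planned total of 320 subjects fail because one subject may carry several of the four products?

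*Protocol*

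**What the plan says.** The size statement in the Subject population row of the protocol reads: "For each Extremity product, the number of inclusions was set at 80, giving a total of 320 subjects for this study". The Implants studies row lists four product ranges: FAST plates, FAST screws, Toe FAST and VEOFIX screws.

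The first product-related inclusion criterion is: "Subject implanted with one or more implants: FAST Screw, FAST Plate, Toe FAST and VEOFIX Screw between November 2021 and October 2022". The non-inclusion paragraph adds that "all implanted patients will be considered", subject to consent. No criterion bars a subject who carries more than one of the four products, and no sentence says how such a subject counts towards the quotas.

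Three other places bear on the point:

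- The rationale gives the regulatory reason for the study: "Regulation 2017/745 requires the collection of clinical data specific to each device".
- Under the secondary endpoints, survival is estimated for each implant, and a revision event is the "removal or replacement of a component of the implant in question".
- The Statistical analysis row rules out tests and plans description only.

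**The concern.** The sentence starts from inclusions per product and ends with a number of subjects. These are the same unit only if each subject belongs to exactly one product. The eligibility text does not guarantee that, so the total could be read as an adding-up error: four groups of 80 that share members do not contain 320 people.

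Two things would be at stake.

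- **Study size.** The number of people enrolled could fall short of 320 although every product quota had been met, and adding up the four groups would count some people twice in a cohort result.
- **Attribution.** The study exists to provide evidence on each device. The AOFAS score and satisfaction are rated for a foot or an operation, so in a subject with two products a result reported by product cannot be credited to one of them.

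**Working it through.** **Inputs.** From the protocol: 4 products (Implants studies) and, in the Subject population row, 80 inclusions per product and a stated total of 320 subjects. Not in the protocol: the share *f* of subjects carrying exactly two of the products. I take *f* = 0, 10%, 25% and 50% as assumptions, with nobody carrying three or four and the overlap spread evenly over the products.

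**Stated figure.** 4 × 80 = 320. It reproduces exactly.

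**Counting under every product carried, 80 as an exact quota.** Product inclusions are fixed at 320, and each subject supplies 1 + *f* of them on average, so distinct subjects N = 320 / (1 + *f*).

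**Counting under one quota only.** Distinct subjects stay at 320. Carriers per product average 320 × (1 + *f*) / 4 = 80 × (1 + *f*).

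| *f* | Every product carried: subjects | Carriers per product | One quota: subjects | Mean carriers per product |
|---|---|---|---|---|
| 0 | 320 | 80 | 320 | 80 |
| 10% | 320/1.10 = 291 | 80 | 320 | 88 |
| 25% | 320/1.25 = 256 | 80 | 320 | 100 |
| 50% | 320/1.50 = 213 | 80 | 320 | 120 |

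The extremes under the first rule are 320 subjects (no overlap) and 80 (everyone carries all four products). If 80 were a minimum per product and not an exact quota, 320 would not be a cap even under this rule.

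**What the table shows.** A stated figure fails only in the second column. Under the one-quota rule, 80 subjects are enrolled for each product and 320 in all, as written. The additional carriers do not contradict an enrolment target of 80; they are further subjects with that device. The amount of data per device, which is what the rationale asks for, is at least 80 subjects under both rules.

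**Subjects carrying one product only.** Under the first rule these number N × (1 − *f*) / 4 per product: about 65, 48 and 27 at 10%, 25% and 50%. Under the one-quota rule they number 80 × (1 − *f*): 72, 60 and 40. These counts matter only if a result is to be credited to one device alone, and the protocol does not say that it will be.

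**Effect on precision, for scale.** The protocol sets no precision target. Taking an illustrative proportion of 80%, the 95% half-width is 1.96 × √(0.8 × 0.2 / n):

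- n = 80: 8.8 percentage points, the same for each product whatever the overlap under the first rule
- n = 320: 4.4 points
- n = 256: 4.9 points
- n = 213: 5.4 points

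So even 50% overlap with product-wise counting widens a cohort interval by about one point.

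**Endpoints against the attribution worry.** Survival is defined per implant, and an event must concern that implant, so a subject with two products contributes correctly to both curves. Consolidation is defined for the cohort, and satisfaction is an overall rating. The AOFAS version depends on implant location, not on product. The endpoint text does not call for AOFAS or satisfaction by product. If such tables were produced, the surgery details listed under Data collected should allow multi-product subjects to be identified.

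**The case for a change.** The strongest case for a change is that the enrolment target and its unit belong to the protocol itself, not to a later analysis document. The sentence derives the total from the quotas, the eligibility text lists four products after allowing several implants, and nothing excludes combinations. A site cannot tell from the text whether a two-product subject fills one place or two, and even a descriptive study needs defined denominators. One sentence would settle it, with no additional patients.

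Part of this stands. The counting rule is not written down, and stating it would be tidy. The rest does not carry the point as far as a correction:

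- The sentence gives its total in subjects, so its inclusions are most naturally enrolments of subjects, each under one product. On that reading nothing is inconsistent.
- The allowance for several implants may refer to several pieces of one product. The remark about considering all implanted patients introduces the consent exception and says nothing about counting.
- Nothing in the protocol shows that combinations occur, or how often. At *f* = 0 the two rules coincide.
- Counting a subject once in cohort results, reporting the overlap and tabulating single-product subjects are matters of analysis sets and tables, which a protocol commonly leaves to the statistical analysis plan.

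**Conclusion.** The concern does not call for a change. The multiplication is right, and under one-quota counting both stated figures hold. Only product-wise counting with an exact quota of 80 turns 320 into a maximum, and the shortfall (29, 64 or 107 subjects at 10%, 25% or 50% overlap) then rests wholly on an assumed share. No test, power or stated precision is affected. Data per device do not drop below 80 carriers under either rule, and survival, the endpoint defined per implant, is already attributed correctly.

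What remains is an unwritten counting rule in a descriptive, non-comparative study. An analyst would count each person once in cohort results and, for implant survival, once for each product carried, using the surgery details already collected. The conclusion assumes that those details identify all the studied products each subject received. It would weaken if AOFAS or satisfaction were to be presented as evidence for single devices and overlap proved common; the protocol states neither.

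### Does fixing 80 inclusions per device, with no stated order for filling them, let centres choose patients whose early results are already known?

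*Protocol*

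**What the plan says.** The Subject population section of the Protocol sets the size: "For each Extremity product, the number of inclusions was set at 80, giving a total of 320 subjects for this study". Inclusion requires implantation of at least one of the four products from November 2021 through October 2022. Under the non-inclusion criteria it says "all implanted patients will be considered", with one further group left out: "Subjects who have not expressed their consent to the collection of their data and participation in the study".

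The Population concerned section is equally broad: "The target population for this study was any adult patient implanted with FAST screws, FAST plates, Toe FAST and VEOFIX screws" in that same period. The rationale gives the purpose: "Regulation 2017/745 requires the collection of clinical data specific to each device".

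The Ethical consideration section dates the start. It records that "CIP and associated procedures obtained an EC approbation on 18/11/2022", "prior to investigation initiation on 07/12/2022". The secondary endpoints include revision of any cause, through a survival curve, and "Complications / effects and adverse events during and after the operation at all follow-up visits".

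Nothing in the document states a consecutive rule, a random draw, centre quotas or a screening log, or says whether 80 is a ceiling.

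**The concern.** A fixed number and an exhaustive population agree exactly only if each device happens to have 80 eligible, consenting patients. If a device has more, someone must decide who is left out.

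The timing is what makes this worth asking. In a prospective cohort, a missing filling order does limited harm, because outcomes are unknown at entry. Here the implantation window had closed before ethics approval. Intra-operative events, early complications and early revisions may already be in the centre's records when it decides whom to approach, and these are study endpoints.

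The study is meant to supply data for each device, and the analysis is descriptive only. If patients were chosen with early results in view, the reported shares and curves would carry that choice and no analysis could remove it.

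**Working it through.** **The plan's own figure.** Four products (FAST plates, FAST screws, Toe FAST, VEOFIX screws) × 80 = 320, as stated. The total is plain multiplication. No power or precision calculation lies behind it that a filling rule could upset.

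**Timing.** The document gives months only, so I take 01/11/2021 to 31/10/2022, which is 365 dates.

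- To initiation on 07/12/2022: 401 days from the first date, 37 from the last.
- To ethics approval on 18/11/2022: 382 days from the first date, 18 from the last.

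Every implantation therefore precedes both dates. This part of the concern is correct.

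**How much of the primary endpoint could be known.** The primary endpoint is an AOFAS score above 80 at 12 months. Patients implanted from 01/11/2021 to 07/12/2021 had reached 12 months by initiation: 37 of 365 dates. With uniform implantation dates, 37/365 = 10.1%. For the other 328/365 = 89.9%, the 12-month score was not yet due. Early complications and revisions could be known for more patients, but elapsed time does not show how many were known.

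**Room for choice.** With N eligible, consenting patients for a device and 80 read as a cap, the number left out is max(0, N − 80). The document does not give N, so these values are assumed:

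| N | Left out |
|---|---|
| 80 or fewer | 0 |
| 100 | 20 |
| 120 | 40 |

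**Extreme bounds, for illustration only.** Assume 80% of the N patients truly score above 80.

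- N = 100: 80 succeed and 20 do not. Leaving out 20 successes gives 60/80 = 75%. Leaving out the 20 failures gives 80/80 = 100%.
- N = 120: 96 succeed and 24 do not. The limits are 56/80 = 70% and 80/80 = 100%.
- N = 80: the share stays at 80%.

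These limits require perfect knowledge of 12-month scores at selection, which the 10.1% figure rules out for most patients. They show what is arithmetically possible and do not estimate bias.

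**The passages read together.** Subject population considers every implanted patient and then removes those without consent. Population concerned takes any adult implanted in the window. Neither gives a licence to pick among eligible patients. On that reading 80 is the planned count per product, and only tracing and consent decide who enters.

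**Whether the obvious repair would settle it.** Suppose each centre approached patients by implantation date until 80 were reached.

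- The 80 applies per product over all centres, so a per-centre order does not determine who fills it without quotas or a central list.
- A strict date order favours the earliest implants, which have the longest known history. With N = 120 and uniform dates, 120 × 37/365 = 12.2 patients had passed 12 months at initiation. All would fall within the first 80, so their share becomes 12.2/80 = 15%, against 10.1% if everyone is included. AOFAS is requested in addition to standard care, so a timely 12-month score may be missing in just these patients.

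**The case for a change.** The strongest case for a change is that entry to the cohort is a protocol matter, not one for a statistical analysis plan. To be considered is less than to be included, and a number that was set needs explaining beside an exhaustive population. Source data verification, as described, checks the patients who were included and does not show who was passed over. Refusals and patients never approached may be unrecoverable unless noted at the time. A sentence and a count sheet would cost little.

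Part of this stands. The document does not say whether 80 is a cap, and the word chosen is weaker than a promise to include everyone. If the sponsor did treat 80 as a cap on a device with many more willing patients, how they were chosen would matter to a reader.

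The rest does not carry the point. It shows an opening that depends on a count the document does not give, not a stated rule that yields a wrong result. The document is a short synopsis and refers to procedures approved alongside it, where a recruitment order or log could lie. Once inclusion is under way, an order cannot be imposed afterwards. What remains is a count of patients included and not included, which a study report commonly carries.

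**Conclusion.** No change to the plan is needed. The dates and the missing filling order are as the concern describes, but the text already leans to including every eligible, consenting patient, and under that reading no choice arises. A selection effect would need two things the document does not establish: that 80 is a cap, and that a device has more than 80 eligible, consenting patients. Its size and direction cannot be derived, and it may be zero.

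The conclusion rests on reading the population statements as exhaustive with 80 as the planned number. The timing figures assume a window running from the first to the last day of the named months, and the 10.1% also assumes uniform implantation dates. This is a gap that centres and analysts can fill sensibly by taking all eligible, consenting patients.

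### All implantations precede inclusion and only consenting patients can enter, so a death before consent cannot appear in the safety data

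*Protocol*

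**What the plan says.** The Population concerned section targets "any adult patient implanted with FAST screws, FAST plates, Toe FAST and VEOFIX screws between november 2021 and october 2022". Under Subject population, the non-inclusion criteria say that "all implanted patients will be considered. However, the following patients will not be included", and then name "Subjects who have not expressed their consent to the collection of their data and participation in the study". The inclusion criteria also require a subject who can understand what the investigator explains, which presupposes a living patient who can be reached.

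Under Ethical consideration, ethics approval is dated 18/11/2022, "prior to investigation initiation on 07/12/2022". The Study schedule opens inclusion once approvals are in hand and estimates this for November 2022.

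Two secondary endpoints bear on the point. The implant-survival endpoint is a 12-month Kaplan-Meier curve with any revision as the event, and adds: "Patients who died or were lost to follow-up will be included in the analysis". The safety endpoint is "Complications / effects and adverse events during and after the operation at all follow-up visits". The Rational section says that the performance and safety data are collected with the aim of "making it possible to confirm the favourable benefit/risk profile for the patient".

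**The concern.** The safety endpoint is meant to start at the operation, but a patient enters only by consenting, and consent could be sought only after the whole implantation window had closed. Anyone who died in between is outside the study. Non-fatal complications and revisions in patients who later consent can still be collected from the records, so the gap on the safety side concerns deaths, together with whatever happened to patients who could not be reached.

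This matters because the study is descriptive and has no comparator, so its safety message rests on absolute rates in a known group of patients. A report of no early deaths would follow from the entry rule and would say nothing about the devices. Without a count of implanted patients who could not enter, a reader cannot tell how far the included subjects represent the patients implanted in the window.

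**Working it through.** The protocol states no figure for the time from implantation to inclusion. The figures below come from its dates.

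**Inputs**
- Implantation window: 01/11/2021 to 31/10/2022, the first and last days of the stated months, giving 365 calendar dates (Population concerned; Subject population).
- Earliest inclusion, reading A: initiation, 07/12/2022 (Ethical consideration).
- Earliest inclusion, reading B: ethics approval, 18/11/2022 (Ethical consideration). This is the more favourable reading, because the Study schedule opens inclusion only after approvals.

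**Step 1: lag = inclusion date minus implantation date**
- Reading A: 07/12/2022 − 31/10/2022 = 37 days; 07/12/2022 − 01/11/2021 = 401 days.
- Reading B: 18/11/2022 − 31/10/2022 = 18 days; 18/11/2022 − 01/11/2021 = 382 days.

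These are minimum lags, since any later consent lengthens them.

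**Step 2: what can be observed.** A death on day t after surgery can appear only if t is greater than that patient's lag. The smallest lag is 37 days (A) or 18 days (B). So no death up to day 37 (A) or day 18 (B) can appear for any subject. This step needs no assumption about event rates.

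**Step 3: illustration under assumptions.** Assume implantations spread evenly over the 365 dates and consent by everyone on the earliest date. Each lag from 37 to 401 (A) or from 18 to 382 (B) then occurs once, and the share of deaths on day t that can appear is the number of lags below t, divided by 365.

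| Day of death | A: consent 07/12/2022 | B: consent 18/11/2022 |
|---|---|---|
| 90 | 53/365 = 14.5% | 72/365 = 19.7% |
| 180 | 143/365 = 39.2% | 162/365 = 44.4% |
| 365 | 328/365 = 89.9% | 347/365 = 95.1% |

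If deaths were also spread evenly over days 1 to 365 (a further assumption), the average share is:
- A: (1 + 2 + … + 328)/365² = 53,956/133,225 = 40.5%, so 59.5% could not appear.
- B: (1 + 2 + … + 347)/365² = 60,378/133,225 = 45.3%, so 54.7% could not appear.

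These are shares of an unknown number of deaths. The protocol gives no death rate, so they do not convert into a count.

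**Step 4: the survival curve.** The Kaplan-Meier event is revision, and death is not an event. A revision before consent in a patient who later consents can be entered at its date. Patients who died or stayed unreachable are missing, but nothing in the protocol says whether their revision risk was higher or lower. Neither the direction nor the size of an effect follows.

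**The case against.** The strongest reply is that the sentence on deaths and losses is not wrong. It sits inside the implant-survival endpoint, where it ordinarily means that enrolled subjects who die or are lost stay in the risk set until that time. The protocol calls itself ambispective, and its non-inclusion criteria openly qualify the intention to consider all implanted patients by requiring consent. A target population need not equal the included sample. All of this stands, and it means there is no flat contradiction in the survival endpoint. What the sentence lacks is a limit to events after inclusion.

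A second reply is that entry rules, censoring and patient-flow counts may be set out in a SAP, and that the consent documents, which were not available for this review, may say more. That is fair for censoring and analysis sets. But who may enter is fixed in the protocol, and no analysis can recover patients who were never included. The point is therefore limited to the protocol as written, which states no exception for patients who died.

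A third reply is that deaths after foot surgery may be few and that no mortality endpoint is defined. The protocol gives no rate either way. Deaths would still belong among complications during and after the operation, and it is there that early ones are ruled out by design.

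**Conclusion.** The point holds for deaths before consent. No death in at least the first 18 days after surgery can be observed, or 37 days if consent began at initiation, and fatal complications can only be under-counted. This rests on the stated dates, the consent rule as printed, and no consent having been taken before ethics approval. The percentages also need the even-spread and single-consent-date assumptions, and they do not give a number of missing deaths.

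Four stronger readings are not supported:
- A reader might infer that implant survival is overstated. The documents do not allow a direction or a size to be derived.
- A reader might infer that no patient lost before inclusion can enter. A patient lost earlier but later reached can consent; only those still unreachable when approached are absent.
- A reader might take 37 days as firm. It is firm only if nobody consented before 07/12/2022.
- A reader might infer, because "the number of inclusions was set at 80, giving a total of 320 subjects for this study", that the quota selects among eligible patients. Nothing says that any product had more than 80.

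The point is worth fixing because it limits what the study can conclude about safety. It does not invalidate the study.

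**What to change.** 1. At each centre, keep an aggregate, non-identifying count per product of patients implanted in the window, known to have died before consent, unreachable, refused, not approached, and included. Report it beside the survival and adverse-event rates.
2. Limit the benefit/risk conclusion to patients alive and consenting at inclusion, and state that deaths before consent were not observable.
3. As a clarification only, add *after inclusion* to the sentence on deaths and losses in the implant-survival endpoint. This changes no estimate.

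The cost is modest work at the centres and a less general conclusion, with no extra patient contact. The sponsor would need to confirm that aggregate counts of patients who did not or could not consent are compatible with the consent rule.
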